3.2 Rationale for Study Design

This study will be conducted in 3 parts: Part A (Initial therapy), Part B (Therapy at 1 and/or 3 mg/kg), and Part C (Therapy at 5 and/or 10 mg/kg). Part A is designed to assess the safety, tolerability, PK, and PD/efficacy of 3 escalating doses of SBC-103 dosed QOW over 24 weeks. As this is the first-in-human study, 24-hour in-patient safety monitoring following the first dose for each subject and SRC and/or Sponsor review of safety data have been incorporated into Part A to minimize risk and to monitor subject safety (see Section 3.1.1.1). Following Part A and prior to entering Part B, subjects will have a 4-week period of time off therapy (instead of the usual 2 weeks between doses that occurs with QOW dosing) in order to assess the impact of reversibility of any observed on-therapy changes in HS.

In light of the pediatric patient population intended for enrollment, it is important (and often required by regulation) to provide some prospect for benefit with the investigational treatment. For an enzyme replacement therapy for a chronic disease such as MPS IIIB, extended treatment is generally required to offer any prospect of benefit. Therefore, Part B is designed to assess the safety, tolerability, PK, and PD/efficacy of chronic dosing for an extended period of time and to allow for intra-patient dose modification based on available data. Prior to commencing Part B, the SRC will review all available safety data from a specific cohort and any safety data available from other cohorts to determine the demonstration of an acceptable safety and tolerability profile to support extended therapy (see Section 7.5). Additionally, in Part B, the SRC will continue to provide oversight of subject safety through periodic reviews of safety data. Ad-hoc reviews of safety data will be performed by the SRC on an as-needed basis in the event of emerging safety signals of clinical concern in one or more subjects, including subjects who meet pre-defined stopping rules (see Section 6.2).

Part C (added with Amendment 6 based on preliminary safety and PK/PD data from Parts A and B) is designed to assess the safety, tolerability, PK, and PD/efficacy of SBC-103 at 5 and 10 mg/kg over at least 24 weeks as well as to assess the effects on chronic dosing. Intrasubject dose modification is permitted in Part C (based on data review and Sponsor agreement) with the intent to treat subjects with the lowest potentially efficacious dose that is safe and tolerable. Because dose escalation occurs in Part C, 24-hour in-patient safety monitoring following the first dose for each subject and SRC and/or Sponsor review of safety data have been incorporated into Part C to minimize risk and to monitor subject safety (see Section 3.1.3.1). Additionally, in Part C, the SRC will continue to provide oversight of subject safety through periodic reviews of safety data. Ad-hoc reviews of safety data will be performed by the SRC on an as-needed basis in the event of emerging safety signals of clinical concern in one or more subjects, including subjects who meet pre-defined stopping rules (see Section 6.2).

To provide the greatest likelihood of benefit, subjects are permitted to enter Part C as soon as necessary regulatory and ethics committee review and approval (where required) has been obtained and the subject meets the qualifying criteria to begin dosing in Part C (see Section 4.3.4). Therefore, each subject's duration of treatment and assessments in Part B may vary. Once a subject enters Part C, the study visit schedule is reset to Day 0 Part C (Day 0C) to ensure that the visit days/assessments correspond to the same number of infusions of SBC-103 for each subject. All study visits in Part C will be scheduled relative to Day 0C to allow for a more meaningful assessment of the PK and PD/efficacy profile of the 5 and 10 mg/kg doses. In addition, subjects will be randomized such that at least 1 subject from each cohort assigned in Part A will receive SBC-103 at 5 mg/kg and at least 1 subject from each cohort assigned in

Part A will receive SBC-103 at 10 mg/kg. Thus each of the assigned dose levels from Part A will be represented in each of the 2 dose levels being studied in Part C.

There are emerging compelling data on the advantages of earlier treatment with ERTs in other MPS subtypes particularly with regard to impact on disease manifestations which are eventually irreversible (Tajima 2013, *Mol Genet Metab*; Gabrielli 2010, *Pediatrics*; McGill 2010, *Clin Genet*; Furujo 2011, *Mol Genet Metab*). Given the inevitable neurodegenerative manifestations of MPS IIIB, early intervention is an important consideration to avoid irreversible disease progression and, therefore, pediatric subjects have been included in this study.

Data from a nonclinical disease model (NAGLU deficient mice) demonstrate reductions in brain HS and increases in brain enzyme activity following IV dosing of SBC-103. Evaluating the accumulation of HS in the CSF via lumbar puncture in this clinical study will provide important insights into the utility of SBC-103 therapy administered IV.

Important manifestations of MPS IIIB disease include developmental and cognitive delay and regression as well as sleep and behavior disturbances. This study includes periodic assessments to evaluate any changes in these parameters after treatment with SBC-103 administered by IV infusion. As noted in Section 1.4.2, structural and diffusion MRI can provide indices of grey and white matter volume reductions and microstructural and white matter connection integrity. For these reasons, structural and diffusion MRI will be used to assess neurodegeneration and any changes after treatment with SBC-103 administered by IV infusion. Blood-brain-barrier integrity will also be evaluated by measuring CSF-AI.

Information regarding the safety and tolerability of each dosing cohort, along with PK/PD data, will be used to guide any additional dose escalation in this study as well as to support the selection of doses and dose scheduling for subsequent studies.

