- A lumbar puncture performed within 4 weeks prior to Study Week 156 may be used as the final assessment for Part C in lieu of performing a lumbar puncture at Study Week 156.

These assessments are also noted on the SOA for Part C.

To provide complete safety data for SRC review (described in Section 3.1.3.1 below), the following subjects will be monitored in an in-patient setting for safety and tolerability as follows:

- The first subject to receive SBC-103 at 5 mg/kg will be monitored for at least 24 hours after administration of the first 5 mg/kg dose.
- The first subject to receive SBC-103 at 10 mg/kg will be monitored for at least 24 hours after administration of the first 10 mg/kg dose.

If a subject discontinues participation from Part C of the study, an additional follow-up phone call will be made 4 weeks after the subject's last administered dose in Part C unless the subject has a scheduled follow-up visit.

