5.1.7 Vital Signs and Electrocardiogram

Vital signs, including pulse rate, respiratory rate, systolic and diastolic blood pressure (BP), and body temperature will be taken at the time points specified in the SOA. In addition, a baseline blood pressure measurement should be taken in triplicate prior to administration of SBC-103 at screening or prior to SBC-103 administration on either Day 0 in Part A or the subject's the next scheduled infusion. The baseline BP measurement should be done as follows:

- Ensure the subject is relaxed or distracted.
- Obtain 3 separate BP measurements.
 - The same arm should be used for each reading.
 - The right arm is preferred for these repeat BP measurements for consistency and comparison with standard tables and, because of the possibility of coarctation of the aorta, which might lead to false (low) readings in the left arm.

- \circ Each reading should be taken on the same day >15 minutes apart.
- The same suitable equipment should be used for each reading.
- Each measurement should be recorded in the subject's source records and in the CRF

On Day 1 in Part A, vital signs will be taken prior to hospital discharge. During dosing visits vital signs will be taken pre-dose (within approximately 30 minutes), approximately every 15 minutes during infusion and approximately every 15 minutes for 2 hours after completion of the infusion. Vital signs should also be obtained after the lumbar puncture is completed as per the standard of care. In Part B, the duration of post-infusion vital signs monitoring may be shortened to 1 hour starting with Week 54, provided that there is no occurrence of IARs during the infusion. In Part C, the duration of post-infusion vital signs monitoring may be shortened to 1 hour starting with Week 26 of Part C, provided that there is no occurrence of IARs during the infusion.

Every effort will be made to collect a 12-lead ECG during the time points specified in the SOA; 12-lead ECGs will be collected in triplicate during Part A of the study only. ECGs will be reviewed by the Investigator, or designee, and any abnormalities will be specified as clinically significant or not clinically significant.

Due to the behavioral issues typical of subjects with MPS IIIB, ECG assessments may not be able to be completed, but should be attempted whenever possible.

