During Infusion							
30 minutes (±5 minutes)	Х	Х	Х	Х	Х	Х	Х
90 minutes (±5 minutes) ^b	X	Х	Х	X	X	Х	Х
120 minutes/End of Infusion ^c (±5 minutes)	X	X	X	X	X	X	Х
After Completion of Infusion ^d							
15 minutes (±2 minutes)	Х	Х	Х	Х	Х	Х	Х
30 minutes (±5 minutes)	Х	Х	Х	X	X	Х	Х
60 minutes (±5 minutes)	Х	Х	Х	Х	Х	Х	Х
90 minutes (±5 minutes)	Х	Х	Х	Х	Х	Х	Х
120 minutes (±5 minutes)	X	Х	Х	Х	Х	Х	Х
4 hours (±5 minutes)	Х	Х	Х	Х	Х	X	X
6 hours (±15 minutes)	X	Х	Х	X	X	Х	X

Key: min. = minutes; Tx = treatment; Wk = Week

^aWeek 130 in Part C or the subject's end-of-therapy visit (ie, Week 156 of the study or early termination visit) ^bTime point may be omitted, if necessary, to avoid exceeding blood volume limitations.

^cAfter the infusion bag has been emptied, but prior to the flush. ^dTime is relative to the end of the infusion, not the end of the flush.

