5.2.5 Telephone Calls

A follow-up telephone call will be made to each subject (or the subject's parent or caregiver) within 24 hours after each of the subject's second, third, and fourth doses (Week 2, Week 4, and Week 6, respectively) in Part A to assess AEs.

If the subject does not participate in Part B or in Part C of the study, an additional follow up telephone call will be made to the subject (or the subject's parent or caregiver) to assess AEs and concomitant medications at least 4 weeks after the subject's last administered dose in either Part A or Part B unless the subject has a scheduled follow-up visit.

If the subject participates in Part C of the study, a follow-up telephone call will be made to the subject (or the subject's parent or caregiver) to assess AEs and concomitant medications at least 4 weeks after the subject's last dose of SBC-103 administered under this protocol unless the subject has a scheduled follow-up visit.

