7.3 Recording of Adverse Events

At each contact with the subject (and the subject's parent or caregiver), the Investigator must seek information on AEs by specific questioning and, as appropriate, by examination. Information on all AEs should be recorded immediately in the source documentation and in the CRF. All clearly related signs, symptoms, and abnormal diagnostic procedures results should be recorded under one diagnosis.

Adverse events will be recorded from the time of signing of the informed consent until completion of the last scheduled visit, ie, the follow-up visit. Adverse events occurring after signing the informed consent but prior to the first dose of study medication will only be recorded if assessed as related to protocol procedures or requirements. Any AEs remaining unresolved should be recorded as ongoing. Ongoing AEs/SAEs should continue to be followed up for the period specified in Section 7.2.2 but without further recording in the CRF. However, follow-up information on SAEs must be reported to the Sponsor or designee as described in Section 7.4.1. Any SAE that occurs after the study period and is considered to be related or possibly related to the study treatment or study participation should be recorded and reported immediately.

Any AE that occurs within 24 hours of the infusion will be recorded by time and date. AEs occurring 24 hours after the infusion will be recorded by date only. The date and time, or the date when the AE started and stopped, as well as the intensity, seriousness, action taken with regard to SBC-103, causality assessment and outcome of the event will be recorded for each AE.

7.4 Reporting of Serious Adverse Events, Infusion-Associated Reactions and Unanticipated Problems

Investigators and the Sponsor must conform to the AE reporting timelines, formats and requirements of the various entities to which they are responsible. (§13 GCP-V; Detailed guidance on the collection, verification and presentation of AE/reaction reports arising from clinical trials on medicinal products for human use ['CT-3']; US CFR Title 21, §312.32, Investigational New Drug [IND] safety reporting). The Sponsor or designee will report all reportable events to all regulatory authorities, IECs or IRBs, and Investigators as required by local regulations.

All SAEs and IARs, and other reportable events (see Section 7.4.3) must be reported to the Sponsor or designee in an expedited manner according to timelines described in Section 7.4.1.

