Adverse Events ¹³	CONTINUOUS														

Page 111 of 121

	Schedule of Study Assessments															
		Pa	rt C: The	apy at 5 a	nd/or 10	mg/kg (Weeks 1	through	26)							
Assessments	Wk 2C	Wk 4C	Wk 6C	Wk 8C	Wk 10C	Wk 12C	Wk 14C	Wk 16C	Wk 18C	Wk 20C	Wk 22C	Wk 24C	Wk 26C			
1 135C55IIICIIIC5		DUC	DIC	-		00	00	100	120	110	100	100	100		10	100
	Visit Window (Days)**	±5		±5	±5	±5	±5	±5	±5	±5	±5	±5	±5	±5	±5	±5
Concomitant Medications ¹⁴		CONTINUOUS														

* The Week 1C Day 1C visit applies only to the first subject at each dose level.

** All study visits will be scheduled relative to Week 1 Day 0 in Part C; infusions must be administered at least 10 days apart.

X^P Assessments to be performed pre-dose.

1. Starting at Week 26C, vital signs will be taken pre-dose (within approximately 30 minutes), approximately every 15 minutes during infusion and approximately every 15 minutes for 1 hour after completion of the infusion, provided there is no occurrence of IARs during the infusion. Vital signs will be obtained after any lumbar puncture as per site standard of care.

- 2. The Vineland-II, BSID-III or KABC-II, BOT-2 Brief Form, and CCC-2 should be administered in-person by an appropriately qualified professional; where possible, the test should be administered prior to dosing.
- 3. Neurocognition testing performed within 8 weeks prior to Day 0 in Part C may be used as the Day 0C baseline in lieu of repeating the assessments on Day 0C.
- 4. The coagulation laboratory panel should be collected within 48 hours prior to performing the lumbar puncture, and the results should be available prior to sedating/anesthetizing the subject or performing the lumbar puncture. The procedure (including the initiation of sedation/anesthesia) will not commence until the site receives these results and confirms that it is safe for the subject to receive anesthesia/sedation and the lumbar puncture. To facilitate this process, all coagulation panels (as of 23 March 2015) will be drawn and analyzed locally rather than sent to the central laboratory for analysis.
- 5. Central lab reference ranges will be used throughout the study, including in the event that labs are analyzed locally. All attempts should be made to draw lab samples for central lab analysis when samples are needed for local analysis.
- 6. If a urine sample is not able to be provided, a serum pregnancy test will be performed by a local laboratory.

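### Protocol Section 3.2 promises every Part C child a 24-hour in-patient stay after the first dose, but the schedule gives it to two of eleven; correct the sentence and add a call at about 24 hours for the rest.

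*Protocol*

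**What the plan says.** **Rationale.** Protocol Section 3.2 introduces the Part C safeguards with "Because dose escalation occurs in Part C, 24-hour in-patient safety monitoring following the first dose for each subject", describes them as incorporated into Part C, and refers to Section 3.1.3.1.

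**Governing text.** Section 3.1.3 is narrower: "The first subject to receive SBC-103 at 5 mg/kg will be monitored for at least 24 hours", with a parallel line for the first child at 10 mg/kg and nothing for anyone else. The footnote to the Weeks 1 to 26 schedule in Appendix D agrees: "The Week 1C Day 1C visit applies only to the first subject at each dose level".

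**Observation of the other children.** Section 5.1.7 sets vital signs on dosing days at "approximately every 15 minutes during infusion and approximately every 15 minutes for 2 hours after completion of the infusion". It allows a shorter period only from Week 26 of Part C. The last Part C sample in Table 7 (Section 5.2.1.3) is at 6 hours after the infusion. The next visit in Appendix D is Week 2C.

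**Telephone calls.** Section 5.2.5 places next-day calls after doses 2 to 4 of Part A only. For Part C it says "If the subject participates in Part C of the study, a follow-up telephone call will be made to the subject", and times that call at least 4 weeks after the last dose.

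**Adverse event collection.** Appendix D marks it as continuous. Section 7.3 adds: "At each contact with the subject (and the subject's parent or caregiver), the Investigator must seek information on AEs by specific questioning".

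**The concern.** Section 3.2 uses nearly the same sentence for Part A, where it is true: Section 3.1.1 keeps every child in for at least 24 hours after the first dose. In Part C it is not true. An ethics committee or site relying on the rationale would credit nine children with a safeguard that the schedule does not give them.

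Behind the wording lies a practical gap. Safety is the primary endpoint, and 5 and 10 mg/kg are doses that no child had received before. For the nine children, an event starting later than about 6 hours after the first infusion at the new dose reaches the record only if the family reports it unprompted, or recalls it when asked at Week 2C. Milder events, and their onset times, are the ones most likely to be lost.

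**Working it through.** **Inputs**
- Part C allocation: 5 children at 5 mg/kg and 6 at 10 mg/kg, 11 in all (Protocol Section 6.7; repeated in SAP Section 9.3.2).
- In-patient stay: 1 child per dose level (Section 3.1.3; Appendix D footnote).
- Recommended infusion time: 2 hours (Section 6.6.2).
- Last scheduled vital signs: 2 hours after the infusion (Section 5.1.7). Last PK sample: 6 hours after (Table 7).
- Week 2C: nominally day 14, window ±5 days (Appendix D), with infusions at least 10 days apart (Section 6.1).

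**Children without the stay.** 5 + 6 = 11, and 11 − 2 = 9. This reproduces the protocol's own count in Section 3.1.3.1, where 4 children remain at 5 mg/kg and 5 at 10 mg/kg: 4 + 5 = 9. As a share, 9/11 = 82%. Scheduled safety contact at about 24 hours therefore exists for 2 of 11 (18%).

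**First day.** Counting the 6-hour PK sample as the last contact, the uncovered part of the 24 hours after the infusion is 24 − 6 = 18 hours, or 18/24 = 75%. This is the lenient count, because the last scheduled safety measurement is at 2 hours. The 4-hour window in the Section 7.1.3 definition of an infusion-associated reaction lies inside the observed 6 hours.

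**Interval to Week 2C, from the 6-hour sample**
- Nominal: 14 × 24 − 2 − 6 = 328 hours = 13.7 days.
- Shortest (10-day spacing): 10 × 24 − 8 = 232 hours = 9.7 days.
- Longest (day 19): 19 × 24 − 8 = 448 hours = 18.7 days.

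**Effect of a call.** A call 24 hours after the infusion leaves 14 × 24 − 2 − 24 = 310 hours, or 12.9 days, to nominal Week 2C. A call at 28 hours leaves 306 hours, or about 12.8 days. The call therefore serves the first day, not the two-week interval. Coverage at about 24 hours rises from 2 of 11 to 11 of 11.

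**Number of calls.** Nine for first Part C doses. If all five children at 5 mg/kg were later escalated, five more: 9 + 5 = 14.

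**Use in dose decisions.** Under Section 3.1.3.1, the decision to give the first 10 mg/kg dose draws on one child's first two doses at 5 mg/kg and on whatever safety data exist from other children already given 5 mg/kg. Expansion at 10 mg/kg rests on the first child's 24-hour data. So at most four of the nine calls, those at 5 mg/kg made before the first 10 mg/kg dose, inform a decision in that section.

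**The case against.** The strongest reply is that the defect is one phrase in a rationale paragraph, apparently carried over from Part A, and that the operative text is consistent. Section 3.3.3 shows the limit to one child per dose is deliberate: it cites prior exposure and the Part A and B safety data. Every child entering Part C has completed at least 4 doses at 3 mg/kg without unmanageable toxicity (Section 4.3.4). Next-day calls were never general: Part A doses 5 to 13 and Part B escalations have none. No planned analysis depends on the call either. The SAP counts any event after the first Part A dose as treatment-emergent, so a late first-day event reported at Week 2C is still counted.

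Most of this stands. The in-patient rule should stay as it is, and the call is not needed to remove the contradiction. But Section 3.3.3 justifies expanding a dose group on one child's data. It does not discuss next-day follow-up of the children then dosed in parallel.

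A reader might infer more than the documents support:
- *The smaller exposure margins at 5 and 10 mg/kg (Table 2) show added risk between 6 and 24 hours.* They are AUC ratios and say nothing about that period. Mean half-life was 0.14 to 0.29 hours (Section 1.4.1.2). If that holds at the higher doses, 6 hours is already more than 20 half-lives (6/0.29 = 20.7).
- *Section 7.3 requires a contact.* It says "Any AE that occurs within 24 hours of the infusion will be recorded by time and date". That is a recording rule for every infusion in the study, nearly all of which have no next-day call.
- *The call closes the gap to Week 2C, or supports every dose decision.* The arithmetic shows neither.

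The safety summary cited from Section 1.4.1.1 and the content of Figure 3 were not available to this review. Whether late first-day events occurred at 3 mg/kg cannot be judged.

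**Conclusion.** The point holds as a certain textual contradiction and a modest gap in solicited safety data. Section 3.2 states a safeguard for each child that the governing text gives to two. Nine of 11 children (82%) have no scheduled safety contact for the last 18 of the first 24 hours after their first Part C infusion. This assumes that all 11 qualify for and enter Part C, that infusions last the recommended 2 hours, and that the 6-hour PK sample counts as a contact.

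The wording correction is needed in any case. The call is a cheap design improvement, justified because safety is the primary endpoint and Section 3.2 itself gives dose escalation as the reason for closer monitoring. It does not rest on evidence of excess late risk, and the number of events it would add cannot be estimated.

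**What to change.** 1. In Section 3.2, replace the reference to each subject with: *for the first subject at each dose level, with a telephone call at about 24 hours for all others*.
2. In Section 5.2.5 and the Weeks 1C to 26C schedule of Appendix D, add one safety call 24 to 28 hours after the end of the first Part C infusion for each child without an in-patient stay, and after the first 10 mg/kg dose of any child escalated from 5 mg/kg. Fix the window, because a call allowed at any time within 24 hours, as in Part A, could come too early to cover the day.
3. Leave Section 3.1.3 and the dosing criteria in Section 3.1.3.1 unchanged.

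The cost is 9 calls, rising to 14 if all five children at 5 mg/kg escalate, with no extra stay, visit or blood draw. SAP Section 4 records that development was stopped in July 2017. Where first Part C doses have already been given, what remains is for the study report to describe the monitoring as it was scheduled, not as Section 3.2 states it.
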